5.4.2 Criteria for discontinuation from the study

Patients may be discontinued from the study at any time. See Section [5.4.4](#) for the procedures for discontinuing a patient from the study. Specific reasons for discontinuing a patient from this study are:

- Voluntary discontinuation by the patient who is at any time free to discontinue his/her participation in the study, without prejudice to further treatment (incapacitated patients may be withdrawn from the study by their legally authorised representative)
- Patient lost to follow-up
- Screening Failures. Note: This is only applicable as a reason for study discontinuation if the patient has not been randomised.

A discussion between the CCC, the Medical Monitor, the AstraZeneca Study Team Physician and the investigator must take place before a patient is withdrawn from the study for reasons other than those specified above.

All patients who die before Day 90 will be classified as completing the study.

5.4.3 Criteria for discontinuation from genetic and/or biomarker research

Specific reasons for discontinuing a patient from the genetic and/or biomarker research are:

- Withdrawal of consent for genetic and/or biomarker research. A patient may withdraw from either of these research sample populations at any time, independent of any decision concerning participation in other aspects of the main study described in this protocol. These patients may continue in the main study providing they have not also withdrawn consent from participation in the main study, and their data will be used in the analysis of the primary and secondary objectives. Voluntary discontinuation by the patient will not prejudice further treatment.

5.4.4 Procedures for discontinuation of a patient from the study

A patient (or legally authorised representative will be asked in the case of incapacitated patients) that discontinues will always be asked about the reason(s) for discontinuation and the presence of any AE. If possible, they will be seen and assessed by an investigator(s). AEs will be followed up (refer to Sections 7.3.3 and 7.3.4). The reason for discontinuation from study drug or from the study must be recorded in the eCRF.

Patients who discontinue study treatment will be given appropriate treatment in accordance with institutional protocol and best practice. Every effort will be made to collect safety data from patients who discontinue.

Discontinuation of patients will be recorded in the Interactive Voice Response System (IVRS).

Procedures for discontinuation from study treatment

Patients who discontinue study drug should remain in the study and continue to have all scheduled assessments as shown in Table 1 (an assessment of all-cause mortality is required at Day 29 [+2] and Day 90, and a blood sample is required at Day 29 [-6/+14]) unless consent is withdrawn for participation in the study.

Procedures for discontinuation from study

In the case of withdrawal from the study, if possible, patients should be seen and assessed by an investigator. At the time of withdrawal, the procedures scheduled for the Day 29 Follow-up Visit should be performed, or Day 90 if the Day 29 Follow-up Visit has already occurred (see Table 1). AEs should be followed up as described in Sections 5.4.2, 7.3.3 and 7.3.4.

5.4.5 Procedures for discontinuation from genetic and/or biomarker aspects of the study

Patients who discontinue from the study should always be asked specifically whether they are withdrawing or continuing their consent for this genetic research or for future biomarker analysis. It must be established whether the patient:

- Agrees to the sample(s) and any DNA extracted from the sample(s) being kept for genetic and/or biomarker research in the future
- Withdraws consent for the sample(s) to be kept for genetic and/or biomarker research in the future and/or wishes the sample(s) to be destroyed. Destruction of the sample(s) (or the DNA extracted from the sample[s]) will only be possible so long as the particular sample(s) is traceable. In the event that genetic and/or biomarker research has already been performed, AstraZeneca will retain the results and associated data for regulatory reasons but these will not be used in any subsequent analyses.

The international co-ordinating investigator is responsible for providing written notification to AstraZeneca of any patient who has withdrawn consent for the use of the sample(s) taken for genetic and/or biomarker research. AstraZeneca will provide written confirmation to the investigator of the actions taken with the sample(s), which must be filed in the investigator study file.

6. STUDY CONDUCT

6.1 Restrictions during the study

The following are prohibited during the study treatment period:

- Immunosuppressant drugs (eg, methotrexate, cyclosporine, tacrolimus).
- Anti-TNF antibodies (eg, infliximab, adalimumab, etanercept) other than study drug.
- If any of the above criteria are fulfilled, the patient must be withdrawn from study treatment in accordance with Section [5.4.1](#)

Patients of reproductive capability must agree to use one of the following forms of contraception throughout the study period and for 90 days after discontinuation of treatment: abstinence, oral contraceptives or other hormonal therapy (eg, hormone implants), intra-uterine device, diaphragm with spermicide or condom with spermicide. It is not known whether AZD9773 interacts with hormonal contraceptives: if female patients are taking hormonal contraceptives to prevent pregnancy then this should be combined with a barrier method of contraception. For males, in the event that a female partner becomes pregnant, due to the unknown risk for the foetus, male partners have the same responsibility with regard to

██████████
contraception.

6.2 Patient enrolment and randomisation

Patient eligibility will be confirmed by the CCC following a telephone interview with the enrolling site. If the patient meets the criteria for participation in the study, the CCC will provide the enrolling site with an enrolment authorisation number. The site will call the IVRS and enter the enrolment authorisation number into the IVRS that will, in turn, enrol the subject. Once enrolled, the pharmacist will be provided with the subject E-code (assigned by the site), the date of birth and the weight. The pharmacist will call the IVRS system that will issue them a randomisation number and allocated treatment for that patient based upon a predetermined randomisation schedule.

The investigative site personnel will:

1. Identify a potential patient and assign a unique screening number.
2. Complete an enrolment authorisation worksheet.
3. Contact the CCC and present the enrolment worksheet information to determine patient eligibility (see Sections 5.1 and 5.2).
4. On obtaining the informed consent, assign an E-code.

The patient E-code will be assigned in chronological order of receiving informed consent and this number will be used throughout the study. If a patient is subsequently not randomised, his or her patient number will not be re-used. Patient E-codes will be 8-digit identifiers, Exxxxyyy, where xxxx is a 4-digit centre identifier and yyy is a 3-digit patient identifier.

5. Be provided with a 5-digit enrolment authorisation number by the CCC if the patient meets all inclusion criteria and no exclusion criteria, and informed consent has been obtained from the patient or their guardian/legal representative.
6. Study centre pharmacists will be provided with patient demographic data (including E-code, date of birth, weight [as taken at screening measured as close as possible to the first dose but within 24 hours before the first dose]) by the investigator and enter the IVRS to receive the randomisation number and allocated treatment for each eligible patient.

If a patient discontinues participation in the study, then his/her enrolment/randomisation code cannot be re-used.

If patients have discontinued their participation in the study then they cannot re-enter into the study.

6.2.1 Procedures for randomisation

Patients will be randomised to treatment following verification of conformance with eligibility criteria at screening. Central randomisation via IVRS will be used to allocate patients to treatment groups (AZD9773: dose 1, dose 2, placebo) in a 1:1:1 ratio and avoid selection bias.

Randomisation will be performed in blocks based on a computer-generated randomisation scheme provided by AstraZeneca. The size of randomisation blocks will not be disclosed to the study centres. Randomisation will not be stratified. The randomisation scheme will randomly assign the study drug to the randomisation numbers.

Randomisation codes will be assigned strictly sequentially as patients become eligible for randomisation. Randomised patients who terminate their study participation for any reason, regardless of whether the study drug was taken or not, will retain their randomisation number. The next patient will be given the next randomisation number.

Patients who are withdrawn after randomisation will not be replaced.

Sections [6.3.1](#) and [6.3.2](#) describes procedures for blinding and breaking the blind.

6.3 Blinding and procedures for unblinding the study

6.3.1 Methods for ensuring blinding

The study will be performed in a double-blind manner. The patient, the investigator and study centre staff will be blinded to study drug allocation. The study centre pharmacist will be unblinded to study drug and will prepare AZD9773 or placebo for a patient as specified by the randomisation scheme and IVRS (pharmacists will call into IVRS to obtain the randomisation/treatment allocation details). All study drug will be blinded using an opaque sleeve, fastened with tamper-evident tape over the iv bag prior to dispensing to other study personnel to maintain the double-blind conditions. Pharmacists will be given specific instructions for study drug preparation and will note if the double-blind conditions have been compromised or the blind broken. All loading doses will be made up to a volume of 250 mL and all maintenance doses will be made up to a volume of 100 mL. Lot numbers of AZD9773 dispensed will be recorded by the pharmacist and monitored by an unblinded monitor. Other study centre staff and monitors will not be given access to lot number information.

Procedures in the case of unblinding by the investigator or designee are described in Section [6.3.2](#).

6.3.2 Methods for unblinding the study

Individual treatment codes, indicating the treatment randomisation for each randomised patient, will be available to the investigator(s) or pharmacists from the IVRS. The process for unblinding will be described in the IVRS user manual that will be provided to each centre.

The treatment code must not be broken except in medical emergencies when the appropriate management of the patient necessitates knowledge of the treatment randomisation. There is

no known antidote to AZD9773, and CCC or the Medical Monitor should be contacted with any concerns. Hence, overdose will not normally be considered a reason for breaking the blind.

If the treatment code is broken then the investigator(s) must document and report to AstraZeneca. AstraZeneca retains the right to break the code for SAEs that are unexpected and are suspected to be causally related to an IP and that potentially require expedited reporting to regulatory authorities. Treatment codes will not be broken for the planned analyses of data until all decisions on the evaluability of the data from each individual patient have been made and documented.

If the blind is broken, the date, time and reason will be recorded in IVRS, and any associated AE report. If a patient's study treatment is unblinded by the investigator or designee, the patient will be withdrawn from study treatment as described in Section 5.4.4.

The IDMC will be provided with unblinded data for their review but AstraZeneca and PAREXEL staff and investigators involved in the study will remain blinded.

6.4 Treatments

6.4.1 Identity of investigational product(s)

Details of the investigational study drug are provided in Table 3. Further information on AZD9773 can be found in the current IB. Doses will be prepared by a pharmacist unblinded to study treatment as specified in the Pharmacist Handling Instructions. All study drug will be blinded using an opaque sleeve, fastened with tamper-evident tape over the iv bag prior to dispensing to other study personnel.

Table 3 **Investigational product**

Investigational product	Dosage form and strength	Manufacturer	Formulation number
AZD9773	5000 units of AZD9773 lyophilised powder/vial for reconstitution in saline and dilution in saline for iv infusion (dose is dependent on treatment arm)	[REDACTED]	F13605
Active Component	AZD9773 (rh TNF α immune Fab [ovine]) [REDACTED]		
Excipients	Di-sodium hydrogen phosphate, USP, Ph Eur Sodium chloride, USP, Ph Eur		
Placebo	0.9% sodium chloride		Not applicable

Vials of AZD9773 will be supplied by AstraZeneca or an AstraZeneca designee to each centre. Study centres will be supplied with sufficient AZD9773 for the study.

Prior to use, AZD9773 must be reconstituted with saline. For iv loading infusions, the reconstituted solution will be diluted to 250 mL of saline solution. For all iv maintenance doses, the reconstituted solution will be diluted to 100 mL of saline solution.

Placebo

Placebo will be saline solution (0.9% sodium chloride) administered as an iv infusion in an equivalent volume to the active treatment (volume of 250 mL for the loading dose and 100 mL for maintenance doses). The pharmacy at each study centre will supply saline for the study.

6.4.2 Doses and treatment regimens

During the treatment period, patients will receive AZD9773 250/50 units/kg or AZD9773 500/100 units/kg or placebo. The first dose of study drug should be administered within 24 hours after confirmation of the onset of qualifying organ failure resulting in severe sepsis and/or septic shock (see Section 5.1 for further details on inclusion criteria). Study drug will be administered by iv infusion.

Each infusion in all treatment arms will be administered over a 30-minute period. Medical management of infusion reactions is detailed in [Appendix D](#). AZD9773 and placebo will be

administered by the investigator or medically qualified personnel in a medically monitored setting. The dose, infusion time and volume remaining for each dose will be recorded in the eCRF together with the date and time of administration (using 24:00-hour clock).

If vasopressors are required during the loading dose, the following should be recorded from 2 hours before the loading dose, during the loading dose and until 30 minutes after completion of the loading dose: name of drug, start date and time, dose, all interim rate changes during administration, route of administration, stop date and time. This applies only to the loading dose.

The body weight measured at screening, measured as close as possible to the first dose but within 24 hours before the first dose, will be the body weight used for all dose calculations during the study. The maximum dose given is based on a 100 kg body weight. If a patient weighs >100 kg, he or she will be given the maximum dose. See [Appendix D](#) for more detailed guidance on handling tolerability.

The last dose may be on Day 5 or Day 6 depending on the start time of the loading dose on Day 1. Dosing should not continue past Day 6.

If necessary, a one-time dosing interval adjustment can be made after the loading dose to create a suitable morning/evening schedule 12 hours apart. The dosing interval adjustment must be such that the first maintenance dose is given a minimum of 6 hours and a maximum of 15 hours after the loading dose. Dosing can be discontinued before all 10 doses are administered if the patient improves and maintains improvement for 24 hours. Improvement is defined as a patient no longer requiring haemodynamic or ventilatory support, no longer requiring ICU admission and there is no evidence of worsening organ failure for at least 24 hours.

Time windows for dosing of ± 2 hours have been factored into the study but it is possible that these windows may be missed or doses given late due to such factors as patient in surgery or X-ray suite, etc. If a dose is late by 2 to 5 hours, the CCC should be contacted first and then the dose should be given immediately. The next scheduled dose should be given at the scheduled time. If a dose is late by over 5 hours, it should be missed and the next scheduled dose should be given at the scheduled time. Below are two example scenarios where the previous dose was given on time but the next dose, dose 6, is late.

Dose No.	Scheduled dose time	Scenario 1	Scenario 2
5	Day 3, 06:00 (given at scheduled time)		
6	Day 3, 18:00	Dose 6 is late and the time is between 20:00 and 23:00 Contact the CCC first and then give this dose immediately	Dose 6 is late and the time is after 23:00 Miss this dose
7	Day 4, 06:00	Give this dose at scheduled time	Give this dose at scheduled time

If a PK sample was scheduled for the missed dose, the PK sample should be taken at the next dose and the actual time that the dose was given and the actual sample time and date should be recorded.

Missed doses will not be replaced.

In the case where a patient stops study drug early because of improvement, protocol assessments including PK should be continued.

6.4.3 Labelling

Labels will be prepared in accordance with Good Manufacturing Practice (GMP) and local regulatory guidelines. The labels will fulfil GMP Annex 13 requirements for labelling. Label text will be translated into local language. Labels will include the following the following information: protocol number, storage conditions, batch identification number, and instructions for dosing; there will be a blank line for the pharmacist to add the patient's enrolment number. The iv bag cover labelling will contain similar information but will exclude the batch number in order to maintain the investigator blinding.

6.4.4 Storage

All study drugs must be kept in a secure place under appropriate storage conditions. The Pharmacist Handling Instructions and the Investigational Product label specify appropriate storage and shelf life.

6.5 Pre-study, concomitant and post-study treatment(s)

6.5.1 Pre-study treatments

Investigators will record all pre-study concomitant medications taken by patients in the 2 weeks prior to patients providing written informed consent for the study. In addition, special attention will be paid to eliciting information about the pre-study therapies listed

below. Patients are not eligible for the study if they have taken any of following within the specified timeframe:

- Immunosuppressants (eg, methotrexate, cyclosporine, tacrolimus) within 2 months before provision of written informed consent for the study.
- High dose steroids (eg, >40 mg or 0.5 mg/kg prednisone or a steroid with equivalent activity, daily for >7 days) within 1 month before provision of written informed consent for the study.
- Currently undergoing active radiation or chemotherapy (including non-cytotoxic) treatment for any type of malignancy (hormonal manipulation therapies for breast and prostate malignancies are permitted).
- Antivenom manufactured using ovine serum, digoxin immune Fab, crotalidae polyvalent immune Fab (ovine), or other parentally-delivered sheep-derived product at any time.
- Anti-TNF antibodies (eg, infliximab, adalimumab, etanercept) within 8 weeks before provision of written informed consent for the study.

6.5.2 Concomitant medications

All medications and aspects of medical management that are standard in the treatment of severe sepsis and/or septic shock as well as any treatment for inter-current diseases will be allowed with the exception of the following during the treatment period (Days 1 to 6):

- Immunosuppressant drugs (eg, methotrexate, cyclosporine, tacrolimus)
- Anti-TNF antibodies (eg, infliximab, adalimumab, etanercept) other than study drug.

Patients requiring immunosuppressant drugs and/or anti-TNF antibodies during the treatment period (Days 1 to 6) will be discontinued from study treatment (see Section 5.4.1). If given during the treatment period or at any time prior to Day 29, the following information should be recorded in the eCRF: name of drug, start date and time, dose, route of administration, stop date and time, from 14 days prior to the loading dose until Day 29.

Drotrecogin alfa (activated) use will be permitted at the discretion of the treating physician. If drotrecogin alfa (activated) is administered, the start date and time, dose, route of administration, stop date and time must be recorded in the eCRF from 14 days prior to the loading dose until Day 29.

For all systemic (parenteral or enteral) anti-infective drugs (antibiotics, antifungals, antivirals, antiparasitics) the following will be recorded: name of drug, start date and time, dose, route of administration, stop date and time, from 14 days prior to the loading dose until Day 29.

If vasopressors are required during the loading dose, the following should be recorded from 2 hours before the loading dose, during the loading dose and until 30 minutes after completion of the loading dose: name of drug, start date and time, dose, all interim rate changes during administration, route of administration, stop date and time. This applies only to the loading dose.

For all other concomitant medications, the following will be recorded: name of drug, start date, route of administration, and stop date from 14 days prior to the loading dose until Day 29.

If the median QTcF is >500 msec at any timepoint, all concomitant medication administered in the 8 hours prior to the ECG will be recorded in the eCRF.

Oral nutrition supplements, total parenteral nutrition, with or without lipids and blood product administration (including whole blood, packed red blood cells, platelets, fresh frozen plasma), will be recorded in the eCRF from randomisation until the end of study treatment.

The administration of all concomitant medication (including IPs) must be recorded in the appropriate sections of the eCRF in accordance with [Table 1](#).

Other medication, which is considered necessary for the patient's safety and well-being, may be given at the discretion of the investigator.

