5.4 Withdrawal of patients

5.4.1 Criteria for discontinuation from the study treatment

Patients may be discontinued from study treatment at any time. Specific reasons for discontinuing a patient from study treatment are:

- Voluntary discontinuation by the patient who is at any time free to discontinue study treatment, without prejudice to further treatment (incapacitated patients may be withdrawn from study treatment by their legally authorised representative).
- AEs (eg, risk to patients as judged by the investigator and/or IDMC, CCC, PAREXEL or AstraZeneca).
- Severe non-compliance to protocol as judged by the investigator and/or CCC, PAREXEL, or AstraZeneca.
- See Section 5.3 for the procedures for handling incorrectly enrolled patients.

- Patient discharged from an adequately monitored setting.
- Positive pregnancy test (except for post-partum).
- Severe reaction to study drug infusion, or progressive, moderate reaction continuing to worsen, or the patient is refractory (eg, moderate reaction which does not respond to treatment) or at the discretion of the investigator ([Appendix D](#)) or study drug is not tolerated.
- Treatment is unblinded by the site investigator or designee.
- Need for immunosuppressant drugs and/or anti-TNF antibodies other than study drug. In the event of the need for these medications, the patient will be discontinued from study treatment but details of the medications (drug name, start date and time, dose, route of administration, stop date and time) will be collected for 28 days from the start of study drug (see Section [6.5.2](#) on concomitant medications).
- Dosing can be discontinued before all 10 doses are administered if the patient improves and maintains improvement for 24 hours (see Section [4.1](#)).

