1. RECOMMENDATIONS FOR IMMUNOSUPPRESSIVE AGENTS

Immunosuppressive Agent ^a	Upper limit dosage use
1. Corticosteroid	
 If for >7 days within 1 month prior to screening/informed consent, a subject has received a mean dose > 0.5 mg/kg/day of prednisone, or the equivalent dose of another agent (see below), the subject is excluded from the study. If a subject has received a mean dose of prednisone (or the equivalent dose of another agent) <0.5 mg/kg/day, the subject will be excluded from the study if their daily dosage exceeds 40 mg/day. 
Adrenal replacement therapy as discussed in the Surviving Sepsis Campaign, up to 300 mg/day of hydrocortisone, will be an allowed exception to this restriction. Steroids, other than hydrocortisone, with greater anti-inflammatory effects (such as prednisone or equivalent) are not the preferred steroid preparation for adrenal replacement therapy in this study.

Equivalent Dose (mg)	
a) Prednisone	0.5 mg/kg/day 40 mg
b) Hydrocortisone	2.0 mg/kg/day 160 mg
c) Methylprednisolone	0.4 mg/kg/day 32 mg
d) Dexamethasone	0.075 mg/kg/day 6 mg
e) Betamethasone	0.06 mg/kg/day 4.8 mg
2. Methotrexate (Rheumatrex, Trexall)	Excluded at any dose.
3. Leflunomide (Arava)	Acceptable if being used as monotherapy.
4. Cyclophosphamide (Cytoxan)	Excluded at any dose.
5. Cyclosporine A	Excluded at any dose. Ophthalmic formulation (Restatis) is permitted
6. FK506 (Tacrolimus)	Excluded at any dose. Topical formulation (Protopic) is permitted.
7. Azathioprine	Excluded at any dose.
8. Cancer Chemotherapy	Patients having received cancer chemotherapy in the previous 4 weeks are excluded.

THIS IS A PRINTED COPY OF AN ELECTRONIC DOCUMENT. PLEASE CHECK ITS VALIDITY BEFORE USE.

Immunosuppressive Agent^a	Upper limit dosage use
9. Mycophenolate Mofetil (MMF) (CellCept)	Solid organ transplant and bone marrow tumour patients. MMF is acceptable if on stable dose.
10. Sirolimus (Rapamycin, rapamune)	Acceptable if on stable dose.
11. Everolimus (Certican)	Acceptable if on stable dose.
12. Thalidomide	Patients receiving this drug within the last 72 hours are excluded.
13. Efalizumab (Raptiva)	Patients receiving this drug within the last 8 weeks are excluded.
Biologics	
(a) Anti-tumour necrosis factor (TNF) agents	Patients receiving anti-TNF agents within the past 8 weeks are excluded.
– Entanercept (Enbrel)	
– Adalimumab (Humira)	
– Infliximab (Remicade)	

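### Appendix I accepts current users of four immunosuppressants whom Section 6.5.1 bars and Sections 5.4.1, 6.1 and 6.5.2 take off study drug

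*Protocol*

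**What the plan says.** **Rules that bar or stop.** Section 6.5.1 lists pre-study treatments that make a patient ineligible, among them "Immunosuppressants (eg, methotrexate, cyclosporine, tacrolimus) within 2 months before provision of written informed consent for the study". Section 6.1 prohibits immunosuppressants and anti-TNF antibodies during treatment and adds: "If any of the above criteria are fulfilled, the patient must be withdrawn from study treatment". Section 6.5.2 sets the period: "Patients requiring immunosuppressant drugs and/or anti-TNF antibodies during the treatment period (Days 1 to 6) will be discontinued from study treatment". Section 5.4.1 gives as a reason for stopping study treatment: "Need for immunosuppressant drugs and/or anti-TNF antibodies other than study drug". None of the four exempts a stable dose or monotherapy, and none refers to Appendix I.

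**Rules that admit.** Exclusion criterion 12 in Section 5.2 names only high-dose steroids and then refers to Appendix I; the overview at the start of Section 5 extends the criterion to other drugs that weaken immunity. Under its heading for immunosuppressive agents, Appendix I says of mycophenolate: "Solid organ transplant and bone marrow tumour patients. MMF is acceptable if on stable dose". Sirolimus and everolimus carry the same stable-dose condition, and leflunomide is "Acceptable if being used as monotherapy". Criterion 11 bars a transplant only within the previous six months.

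**How the rules are used.** Section 6.2, step 3, has the Clinical Co-ordinating Centre (CCC) decide eligibility from Sections 5.1 and 5.2. Section 13.2.3 counts failed entry criteria and drugs prohibited under Section 6.5.2 as important deviations. Section 13.1 uses the per-protocol population for all efficacy summaries and analyses, with an ITT analysis in addition.

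**The concern.** A condition such as "acceptable if on stable dose" can only describe someone who is taking the drug now. Appendix I therefore admits current users, while the body of the protocol treats current use as a bar to entry and a reason to stop dosing. A site and the CCC that follow Sections 5.1, 5.2 and Appendix I correctly would authorise a patient whom Section 6.5.1 calls ineligible.

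Three things depend on which text is applied: whether the patient enters, whether the patient is dosed, and whether the patient counts in the population used for the main efficacy analysis. With about 100 centres, identical patients could be handled differently. Section 6.2.1 does not replace withdrawn patients, so a patient admitted and then stopped stays in ITT with an incomplete course.

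**Working it through.** **Step 1: one patient through every rule.** Take a patient on stable mycophenolate whose solid organ transplant was more than six months ago and who otherwise qualifies.

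| Place | Rule | Result |
|---|---|---|
| 5.2, criterion 11 | Transplant within 6 months | Not excluded |
| 5.2, criterion 12 | High-dose steroids; refers to Appendix I | Goes to Appendix I |
| Appendix I, item 9 | Stable dose accepted | Accepted |
| 6.2, step 3 | Check against 5.1 and 5.2 | Can be authorised |
| 6.5.1 | Use within 2 months | Ineligible |
| 6.1 | Prohibited during treatment | Must be withdrawn from study drug if mycophenolate continues |
| 5.4.1 and 6.5.2 | Need for an immunosuppressant | Stopped |
| 13.2.3 | Drug prohibited under 6.5.2 | Important deviation, out of per-protocol |
| 5.3 | Found ineligible after randomisation | Stopped only if there is a safety concern |

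The fourth and fifth rows cannot both be followed. The last row adds a further clash: if failing Section 6.5.1 counts as failing the entry criteria, Section 5.3 restricts stopping to safety concerns, whereas Section 6.1 makes withdrawal mandatory.

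**Step 2: how many agents.** Appendix I numbers 13 agents before its biologics. Four non-steroid agents are accepted in current users: items 3 (leflunomide), 9 (mycophenolate), 10 (sirolimus) and 11 (everolimus). Sections 6.5.1 and 6.5.2 exempt none. The three drugs that Sections 6.1, 6.5.1 and 6.5.2 give as examples (methotrexate, cyclosporine, tacrolimus) are items 2, 6 and 5 in some order, and Appendix I rules out all three whatever the dose, apart from ophthalmic or topical forms. Item 12, thalidomide, has a 72-hour window against two months in Section 6.5.1, so a patient whose last dose lies between those limits passes one rule and fails the other.

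**Step 3: dose lost if stopped.** The full course is 250 + 9 × 50 = 700 units/kg in arm 1 and 500 + 9 × 100 = 1400 units/kg in arm 2. The loading dose is 250/700 = 500/1400 = 36% of it. A stop straight after loading loses 64%; a stop before dosing loses 100%. These stop times are illustrations, not predictions.

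**Step 4: power.** Section 13.4 gives SD 11.380, difference 4.2 days, 100 per group, one-sided 10% and 90% power. For a two-sample t-test, the non-centrality is 4.2 / (11.38 × √(2/n)). At n = 100 this is 4.2/1.609 = 2.61 and power is 0.9070, which reproduces the plan's figure. The share of affected patients is not in the document. Assuming purely for scale that 1% to 5% of each arm leaves the per-protocol set, power is 0.9048 at n = 99 and 0.8955 at n = 95.

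**The case against.** The best defence is that Sections 6.1, 6.5.1 and 6.5.2 illustrate the banned class with three drugs, and Appendix I bars all three. Appendix I could then be the detailed definition of the class, and only a cross-reference would be missing. This does not resolve the conflict: the three drugs are given as examples of a class, Appendix I puts the four accepted agents under the same class heading, and none of the body sections refers to it. The narrower reading has to be inferred.

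A second defence is that Sections 5.4.1 and 6.5.2 speak of a need for, or requiring, these drugs, which could mean a need that arises on study. The plain prohibition in Section 6.1 does not allow that reading.

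A third is that Appendix I is presented as recommendations, and that its first item, corticosteroids, shows that its classification is not the body's: Section 6.5.1 and the Table 1 footnotes list steroids separately from immunosuppressants. This part stands. Counting steroids below the dose limit, current users of five of the 13 agents would be acceptable. It shows that the sponsor must say which classification governs; it does not take the four agents out of the class.

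Safeguards also count for something. The CCC reviews each patient by telephone, Section 5.3 requires a documented discussion of wrongly included patients, and per-protocol exclusions are agreed before code break. These steps limit unnoticed inconsistency and guard against bias by arm, but none says which rule holds, and the last comes after dosing has been affected.

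A reader might go further and infer a material loss of power, bias between arms, or that stopped patients receive almost none of the course. The documents support none of these: no prevalence is given, the assumed range barely moves power, nothing in the conflict depends on the arm, and the loading dose alone is 36% of the course.

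**Conclusion.** The conflict is between operative rules in one document and stands on the text. Current users of four of the 13 numbered agents are accepted by Appendix I, ineligible under Section 6.5.1 and, if they continue the drug on Days 1 to 6, stopped under Sections 5.4.1, 6.1 and 6.5.2 and left out of per-protocol under Section 13.2.3. Thalidomide adds a mismatch of windows. The conclusion assumes that the four agents are immunosuppressants in the body's sense, as the Appendix I heading indicates.

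The number of such patients is not stated and is probably small. The effect is on who may enter, who is dosed and who is in the per-protocol population; power is not a ground for the change.

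A reader might also infer that the corticosteroid wording in Section 13.3.1, which implies that steroids other than adrenal replacement stop study drug, is a stray phrase that can be deleted. The documents do not support that. No stopping rule says so, but the exception matches the hydrocortisone exception in Appendix I, so the phrase may record what the sponsor intended.

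**What to change.** Use one rule throughout. The sponsor should choose between two options on safety grounds, bearing in mind that the study drug is itself an anti-TNF agent.

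- **(a) Full ban.** Remove the acceptances of leflunomide, mycophenolate, sirolimus and everolimus from Appendix I, align the thalidomide window, and put the two-month rule of Section 6.5.1 into exclusion criterion 12, so that the Section 6.2 check reaches it.
- **(b) Appendix I governs.** Refer Sections 5.4.1, 6.1, 6.5.1, 6.5.2 and 13.2.3 to Appendix I. State that an accepted agent already taken at entry under the Appendix I condition may continue and is not an important deviation, and that a new start on Days 1 to 6 stops study drug.

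Keep the corticosteroid phrase in Section 13.3.1 for now. The sponsor should first confirm whether non-replacement steroids are meant to stop study drug, and then align Sections 6.5.2 and 13.3.1.

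The cost is a wording amendment. Option (a) also narrows eligibility slightly. Endpoints, analysis model and sample size do not change.
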